#### 4.5.3. Movement imagery Questionnaire, revised (MIQ-RS)

The MIQ-RS questionnaire (Gregg et al, 2010) consists of 2 subscales, one visual and the other kinesthetic, with 7 items each, with each item scored on a 7-point Likert scale (the higher the score, the higher the score). ease to imagine). For all items, the user is asked to perform a specific motor act (only once), return to the starting position, and then imagine it. When scoring the visual scale, the participant is asked to generate an image "as if it were seen" by making the gesture, while the kinesthetic scale is asked to "remember the sensation of the movement."

The administration manual specifies that the visual and kinesthetic items will not be administered consecutively, but rather are altered randomly to avoid bias.

The minimum values are 14, and the maximum values are 98 (minimum 7 and maximum 49 for the subscales).

This MIQ-RS version was made to be administered to a population with some type of physical disability, but it can also be applicable to healthy people. The Spanish version of the MIQ-RS has been validated by Cantalejo-Fernández (2022) in a sample of university students, obtaining Cronbach's Alpha values of 0.90 and a two-factor structure.

#### **4.6. Description of the intervention.**

As explained, the study will consist of 4 groups.

Each group will receive a total of 5 sessions (Figure 1). Next, it is explained what each of the 4 groups will do.

4.6.1 Control group: This group will not receive any type of intervention and will continue with their usual routine. A commitment will be requested that they do not begin any physical activity other than that previously carried out for the duration of the study.

#### 4.6.2 FESIA GRASP Group:

There will be 5 30-minute sessions, and the 2 available protocols will be used: training and grip.

Protocol 1: Training: It will be

used during the first half of the first session so that the participant becomes accustomed to the sensation of electrical stimulation through an automatic sweep of electrical stimulation.

Protocol 2: Grip

It will be used in sessions 1-5, both inclusive. Firstly, the device configuration will be carried out, selecting the combinations of cathodes that generate clearer flexion and extension movements of the wrist, thumb, index and fingers 3, 4 and 5. If the motor threshold is not found in any user for any of the movements, or it is considered that it may be harmful or not beneficial to stimulate any of these, it will not be selected. It will be important to do this setup thoroughly in the first session, and minor variations will be made in subsequent sessions.

Next, the therapy will begin. This will progress as follows (it will be adjusted depending on the patients' progress):

- Sessions 1-3: selective contractions of the forearm muscle groups.
- Weeks 4-5: training in activities of daily living with the help of FES

The general development proposed during sessions 1-3 is as follows:

- Startup (5 minutes): Place the device and verify that the previous configuration is correct.

- First part (5 minutes): selective contractions of the different groups muscles through FES.
- Second part (10-15 minutes): voluntary selective contractions by the

patient, guided by the therapist.

The general development proposed during sessions 4-5 is as follows:

- Startup (5 minutes): placing the device and verifying that the previous configuration is correct.
- First part (5 minutes): selective contractions of the different groups muscles through FES.
- Second part (10-15 minutes): inclusion of functional movements previously activated in functional actions through FES: grasping objects of different sizes.

The selected electro-parameters will be those preconfigured by default in the systems from Fesia, both in the training protocol and in the grip protocol: 25 Hz frequency, 250 us pulse width. The intensity will be 5 mA above the motor threshold, the motor threshold being the minimum intensity at which the movement of the limb is perceived visually. If the patient cannot tolerate such intensity, he will limit himself to the maximum intensity at which this sensation is pleasant.

Therapy times will vary depending on the patient's fatigue measured using a Borg scale. The score for this should not exceed 3 points out of 10 ( $\leq 3/10$ ), 1 minute after the end of the exercise. If the perception of fatigue is greater, first the intensity (eg frequency of movements) and then the duration of the therapy will be adjusted.

#### 4.6.3. Globus Elite Electrostimulator Group:

You will also carry out 5 sessions of 30 minutes duration. The device will be applied in the following way (it will be adjusted depending on the patients' progress):

- Sessions 1-3: general repetitive contractions of the muscle groups of the forearm.
- Weeks 4-5: training in activities of daily living with the help of FES

The general development proposed during sessions 1-3 is as follows:

- Startup (5 minutes): Place the device and verify that the configuration is correct.
- First part (5 minutes): general contractions of the different groups muscles through FES.
- Second part (10-15 minutes): general voluntary contractions by the patient, guided by the therapist.

The general development proposed during sessions 4-5 is as follows:

- Startup (5 minutes): Place the device and verify that the • configuration is correct.

- First part (5 minutes): general contractions of the different groups muscles through FES.
- Second part (10-15 minutes): inclusion of functional movements previously activated in functional actions through FES: grasping objects of different sizes.

The electro-parameters selected will be the same as those used in the previous group.

Therapy times will vary depending on the patient's fatigue measured using a Borg scale. The score for this should not exceed 3 points out of 10 ( $\leq 3/10$ ), 1 minute after the end of the exercise. If the perception of fatigue is greater, first the intensity (eg frequency of movements) and then the duration of the therapy will be adjusted.

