The Fesia Grasp system is a FES-based neurological hand rehabilitation device developed by Fesia Technology (Donostia-San Sebastián, Spain). This is a commercial device designed for manual dexterity rehabilitation, which delivers a train of biphasic pulses of different widths and amplitudes to different electrode fields asynchronously, meaning that different electrode fields are activated with an interval predefined between pulses Malešević et al (2017).

Fesia Grasp, generates superficial electrical stimulation of the forearm muscles to trigger eight different flexion and extension movements of the wrist and fingers in order to restore the function, freedom and independence of the patient's hand after a stroke, Martin -Odriozola et al (2021).

The study aims to answer the PICO research question:

Q: healthy adults

I: FES and, multfield FES.

C: video games

O: Motor imagination, strength, manual dexterity.

The aim is to compare different tools in a population sector to check if there is an improvement in motor skills through the use of FES.

2.- Objectives

General objective:
 
 
• Check the effects of FES and virtual reality regarding motor imagination, strength and manual dexterity.
 
 
Secondary objectives:
 
 
• Find out if functional electrical stimulation improves motor imagination, both kinesthetic and visual, as well as manual dexterity and strength.
 
• Find out if an intervention based on the use of virtual reality improves motor imagination, both kinesthetic and visual, as well as manual dexterity.
 
• Check if there are differences between FES, multi-field FES, and virtual reality in terms of visual motor imagination, kinesthetic and manual dexterity.
 

3.- Project description

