
The present work is a clinical, randomized study of parallel groups of a quasi-experimental type.
 
A sample of university students will be divided into 4 groups, where one of them will act as a control group (without intervention), and the other three will perform hand training with two different types of FES devices (conventional and multi-field). and a last group will receive hands-on training with video games.
 
Intergroup analyzes will be performed before the start of training (pre-intervention), after finishing the program (post-intervention), and three weeks after finishing (follow-up evaluation). Likewise, intragroup analyzes will be carried out to check whether the training has caused an improvement in the quality of motor imagination, as well as an improvement in manual dexterity in each of the groups.
 
To carry out the project, a collaboration agreement will be signed with the company FESIA TECHNOLOGY SL, which will provide a FESIA GRASP device for the study, as well as the consumables (electrodes) necessary for the development of the study. The agreement is currently being evaluated by the UBU legal office.
 
It is planned to register the study on the international platform Clinicaltrials.gov.

4.- Material and methods

4.1 Type of study
 
Controlled, randomized, parallel group clinical trial. Unicentric, and with blind evaluation by third parties. Quasi-experimental.
 
4.2. Description of devices
 
Four parallel groups are planned. A first group that will have an intervention based on multi-field FES with the FESIA GRASP device; another group that will receive only FES

with the Globus Elite electrostimulation device (device with conventional electrodes); a third group that will receive an intervention based on virtual reality; and finally a control group, which will not receive any treatment.

The three devices are described below.

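### In sessions 1-3 the two FES arms get different voluntary exercise, so a difference between multi-field and conventional FES cannot be attributed to the electrode type

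*Combined protocol and SAP*

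**What the plan says.** Section 2 lists as its third secondary objective: "Check if there are differences between FES, multi-field FES, and virtual reality in terms of visual motor imagination, kinesthetic and manual dexterity". Section 3 describes the two stimulation arms as "hand training with two different types of FES devices (conventional and multi-field".

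Much is matched between these arms. Both have five 30-minute sessions, the same Borg fatigue rule, and the same wording for the second part of sessions 4-5. On stimulation settings, section 4.6.3 states: "The electro-parameters selected will be the same as those used in the previous group".

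Sessions 1-3 differ. For the multi-field arm, section 4.6.2 gives the overall content as "Sessions 1-3: selective contractions of the forearm muscle groups" and the longest block as "Second part (10-15 minutes): voluntary selective contractions by the" patient, under therapist guidance. For the conventional arm, section 4.6.3 gives: "Second part (10-15 minutes): general voluntary contractions by the patient, guided by the therapist".

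Section 4.6.2 also has an automatic stimulation sweep, "used during the first half of the first session so that the participant becomes accustomed to the sensation of electrical stimulation". Section 4.6.3 has no counterpart. Section 10 plans inter-group analyses without naming a method or separating device from exercise content.

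**The concern.** Each of sessions 1-3 has a first part delivered through FES and a second part described as voluntary. Selective evoked contractions are a feature of the multi-field electrode (section 4.2.1), so the difference in the first part belongs to the device contrast. The voluntary part is different. Selective or general voluntary contractions can be performed on instruction in either arm, and no section explains why the arms are given different kinds.

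Every multi-field participant gets one kind of exercise and every conventional participant the other. Randomisation balances the participants, not the programme. Blinded evaluation protects the measurement. Neither these nor any covariate adjustment can separate exercise content from electrode.

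What is at stake is the sentence the trial may write at the end. A difference between the FES arms could be reported as an effect of the multi-field electrode when part of it may come from the exercise. The maker of the multi-field device supplies it and its consumables (section 3), so such a claim would be examined closely.

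**Working it through.** The plan states no figure for this contrast, so there is none to reproduce. The check is a side-by-side reading and a sum of scheduled minutes.

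**Side by side (sections 4.6.2 and 4.6.3)**

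| Element | Multi-field arm | Conventional arm | Reading |
|---|---|---|---|
| Sessions | 5 of 30 min | 5 of 30 min | matched |
| Electrical parameters, Borg rule | stated | same | matched |
| First part, all sessions (5 min) | selective, by FES | general, by FES | part of the device contrast |
| Second part, sessions 1-3 (10-15 min) | voluntary, selective | voluntary, general | differs, independent of electrode |
| Second part, sessions 4-5 (10-15 min) | functional, with FES | same wording | matched |
| Sweep, first half of session 1 | yes | none stated | unmatched stimulation exposure |

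**Size of the voluntary block.** The inputs are the stated timings, with the second part assumed equally long in every session.

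- Voluntary block: 3 × 10 = 30 min to 3 × 15 = 45 min.
- Scheduled time: 5 × 30 = 150 min. Share: 30/150 = 20% to 45/150 = 30%.
- Itemised active time (first and second parts, without startup and the sweep): 5 × (5 + 10) = 75 min to 5 × (5 + 15) = 100 min. Share: 30/75 = 40% to 45/100 = 45%.
- Within sessions 1-3: 10/15 = 67% to 15/20 = 75% of itemised active time.

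**Session 1 of the multi-field arm**

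- Sweep: half of 30 min = about 15 min.
- Itemised content: 5 + 5 + 10 = 20 min to 5 + 5 + 15 = 25 min.
- Sum: 15 + 20 = 35 min to 15 + 25 = 40 min, against a stated 30 min.

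If the 30 minutes hold and startup and first part keep their length, 30 − 15 − 5 − 5 = 5 min is left for the voluntary block, instead of 10-15. The multi-field total would then be 5 + 2 × 10 = 25 min to 5 + 2 × 15 = 35 min. The arms could thus differ in the amount of voluntary exercise as well as its kind. The text does not say which timing applies.

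**The case against.** The strongest reply is that the plan never promises an electrode-only contrast. The objective names virtual reality in the same sentence, and that arm differs in all its content. Section 1 speaks of comparing tools, and section 10 of comparing interventions. On that reading two complete programmes are compared, and a voluntary block that mirrors each device's evoked contractions is a coherent design. This largely stands: the comparison of programmes is valid. It does not support attribution to the electrode, which the framing as two device types and the matched electrical parameters invite.

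It can also be said that both arms do therapist-guided voluntary work for the same stated time, and that only one undefined adjective differs. This stands as a limit on size: the 30-45 minutes are the length of the block, not a measure of how far its content differs.

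Three stronger readings may tempt a reader, and the documents support none of them:

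- **That the bias favours the multi-field arm.** Selective practice might seem closer to the peg test, but no section shows this. If the sweep displaces practice in session 1, that element could act the other way.
- **That the sweep is device-free training, or simply adds 15 minutes.** It is electrical stimulation, one of the device's two protocols, and sessions last 30 minutes in both arms.
- **That sections 4.6.2 and 4.6.3 contradict each other.** They describe different arms. The internal conflict is the session 1 timing within section 4.6.2.

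**Conclusion.** The point holds for attribution. A difference between multi-field and conventional FES under the third secondary objective cannot be assigned to the electrode type, because therapist-guided voluntary exercise also differs in three of the five sessions. The contrast remains usable as a comparison of two training programmes.

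The shares given above rest on the itemised timings being followed. The plan allows therapy times to vary with fatigue, so delivered minutes may differ. The share of scheduled time is the more cautious figure, since the larger one leaves out startup, the sweep and time the plan does not itemise. How much of any observed difference would come from the exercise cannot be derived from the documents.

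The familiarisation sweep is a separate and lesser matter: a stimulation exposure given to one arm only, within a session whose stated parts exceed its stated length.

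**What to change.** 1. In sections 4.6.2 and 4.6.3, use one common script for the voluntary block of sessions 1-3 in both FES arms: same movements, order, repetitions and therapist instructions. The content is for the sponsor to choose. The FES-evoked part can go on differing with the device.
2. Reconcile the session 1 timing in section 4.6.2 (sweep, itemised parts and session length), and either reconcile or justify the familiarisation difference between the arms.
3. If the voluntary contents stay different, reword the third secondary objective as a comparison of two training programmes, give the reason for the difference, and make no claim about electrode type.

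The cost is protocol wording and one shared therapist script, with no extra sessions, staff or participants. The small downside is that in one arm the voluntary block no longer mirrors that device's evoked contractions. The script has to be settled before the first intervention, because no later analysis can separate content from arm.

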#### 4.6.4. Rehab Hands Virtual Group

The group will play for 5 30-minute sessions. The Virtual Rehab Hands device includes fine motor games thanks to an ergonomic support to rest the arm and be able to perform the exercises more comfortably with the Leap Motion® sensor that accurately detects the movements of the hands, fingers and wrists.

The session will be divided into three phases: warm-up, effort and return to calm.

- In the warm-up phase, "wrist flexion and extension bird" will be played; "candy flexion and extension"; "ulnar-radial deviation frog"
- In the effort phase: "digital piano"; "balloon clamps"; "finger abduction"
- In the phase of returning to bed: "flexion-extension frog"; "flexion and extension bird wrist".

#### **4.7. List of expected adverse events**

During the course of the proposed study, all adverse effects will be registered.

Every effort will be made to remain alert to potential complications and unexpected results. If complications occur, the first concern will be the safety of the participant.

Intensive use of the Fesia Grasp product may entail a series of risks (described below) that will be minimized by taking their respective precautionary measures:

- Electrical stimulation may cause an uncomfortable sensation or very mild pain in the first few uses until you become familiar with the sensation.

- It is normal for the area where the stimulation has been applied to appear red after removing the device; this redness should disappear in approximately one hour.
- In some cases, electrical stimulation or contact of the gel with the skin could cause an allergic reaction or irritation at the contact surface.

The patient must immediately stop using the device in the following cases:

- You have redness or irritation in the stimulation application area for more than one hour after removing the electrode.
- Presents blisters or sores in the stimulation application area.
- You feel cardiac stress or tachycardia during pacing.
- You have swelling of the leg, knee, ankle or foot.

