#### **6.- Determination of the potential benefits and risks of the study**

The participation of the subjects in this project implies the eventual possibility of suffering adverse effects, none of which seriously compromise the integrity of the subject. Every effort will be made to remain alert to potential complications and unexpected results. If complications occur, the first concern will be patient safety.

The intensive use of FES can entail a series of risks (described below) that will be minimized by taking their respective precautionary measures:

- Electrical stimulation may cause an uncomfortable sensation or very mild pain in the first few uses until you become familiar with the sensation.
- It is normal for the area where the stimulation has been applied to appear red after removing the device; this redness should disappear in approximately one hour.
- In some cases, electrical stimulation or contact of the gel with the skin could cause an allergic reaction or irritation at the contact surface.

The patient must immediately stop using the device in the following cases:

- There is redness or irritation in the stimulation application area during more than one hour after removing the electrode.
- Presents blisters or sores in the stimulation application area.
- You feel a significant increase in muscle spasticity.
- You feel cardiac stress or tachycardia during pacing.
- Presents swelling in the extremity.

Regarding the collection of data on motor function, this is carried out using non-invasive techniques so they do not pose any risk to the participant.

The benefits that the subject obtains in this project are the motor improvement and functionality of the upper limb, as well as a direct contribution to the advancement of knowledge of new techniques or therapies for their pathology.

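### The device-stop lists in sections 4.7 and 6 differ on swelling, and section 4.7 names only lower-limb sites although both stimulation devices act on the forearm

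*Combined protocol and SAP*

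**What the plan says.** Section 4.7 introduces its risks with "Intensive use of the Fesia Grasp product may entail a series of risks". It then gives a mandatory instruction, "The patient must immediately stop using the device in the following cases", followed by four items. Three concern prolonged redness or irritation, blisters or sores, and cardiac symptoms during stimulation. The fourth is "You have swelling of the leg, knee, ankle or foot".

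Section 6 introduces its risks with "The intensive use of FES can entail a series of risks" and repeats the same mandatory sentence, this time with five items. The same three appear. The swelling item is now "Presents swelling in the extremity", and there is one further item, "You feel a significant increase in muscle spasticity".

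On where the current is applied, section 1 says that Fesia Grasp "generates superficial electrical stimulation of the forearm muscles". Section 4.2.1 describes an electrode laid over the forearm. Section 4.6.3 has the Globus device contract the forearm muscle groups and adds: "The electro-parameters selected will be the same as those used in the previous group". The inclusion criteria in section 4.3.2 ask for intact skin on the arm that will carry the device.

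**The concern.** A stop rule should be usable as written by the person running the session. Section 4.7 comes straight after the descriptions of the interventions and is a natural place for an operator to look. Its swelling item names four parts of the lower limb, none of which is stimulated in this trial. Swelling of the forearm or hand carrying the electrode meets no item in that list.

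Section 6 can be read to cover that event, so two lists of equal force are in the protocol and they differ on it. An operator working from section 6 may stop the device where one working from section 4.7 has no listed reason to. What is at stake is participant safety and the consistency of stopping. Consistency also bears on follow-up, because section 4.3.2 lets participants leave the study when adverse events prevent them from continuing.

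**Working it through.** There is no figure to reproduce and no formula applies. The check sets the two lists side by side and then compares the swelling item with the stimulated site.

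**Step 1: the two lists, item by item.**

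| Item | Section 4.7 | Section 6 | Result |
|---|---|---|---|
| Redness or irritation beyond one hour | yes | yes | agree |
| Blisters or sores | yes | yes | agree |
| Cardiac stress or tachycardia | yes | yes | agree |
| Swelling | leg, knee, ankle, foot | extremity, limb not named | differ in site |
| Marked rise in spasticity | no | yes | section 6 only |
| Number of items | 4 | 5 | 3 agree, 1 differs, 1 is extra |

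**Step 2: the swelling item against the stimulated limb.** Sections 1 and 4.2.1 put Fesia Grasp on the forearm. Section 4.6.3 puts Globus on the forearm. Section 4.3.2 speaks of the arm where devices are placed. No section describes lower-limb stimulation. The item in section 4.7 therefore covers no part of the stimulated limb. The item in section 6 can cover the arm, though it does not name it.

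**Step 3: one event under both lists.** Suppose the stimulated hand swells. Section 4.7, read literally: no item met. Section 6: the swelling item can be met, and the device must be stopped at once.

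**Step 4: does scope explain the difference?** Section 4.7 is framed around one product and section 6 around FES in general. Section 1 describes Fesia Grasp as an FES-based device, so both lists apply to that arm and still differ. Sections 3 and 4.2 describe the Globus arm as FES, so section 6 reaches it, while section 4.7 does not mention it.

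**Step 5: how many participants the rule governs.** Section 4.3.2 expects 20 to 25 per group. Two stimulation arms give 2 × 20 = 40 to 2 × 25 = 50. This is the number under the rule, not a number expected to have an event; no event rate is given.

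**The case against.** The strongest reply is that the lists do not conflict in the strict sense. Neither claims to be exhaustive, nothing in one forbids what the other requires, and an operator who follows both will stop whenever either says so. Section 6 is in the same document and carries the same force. Section 4.7 itself tells staff to watch for complications and puts the participant's safety first. All of this stands, and it limits the point: the gap arises when section 4.7 is read alone. It does not remove the point, because a general call for vigilance is not a specific trigger, and the item in section 4.7 still names a limb that is not treated.

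Three stronger readings are tempting, and the documents do not support them.

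- A reader might infer that adverse events would be recorded differently by operator or by arm. Section 4.7 says that all adverse effects will be registered, with no limit by device or list, and section 4.3.2 has the reason for leaving recorded.
- A reader might infer damage to a safety comparison of the two devices. The objectives in section 2 concern motor imagination, strength and dexterity, and section 10 plans no safety analysis.
- A reader might infer that the Globus arm has no stop rule, or that the spasticity item is a second contradiction. Section 6 covers FES in general and so reaches Globus. Spasticity is an omission from one list, and its practical weight is small in healthy adults from whom neuromuscular pathologies are excluded by section 4.3.2. Both are side notes.

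**Conclusion.** The point holds in a narrow form. The swelling item in section 4.7 is wrong as written for a trial that stimulates only the forearm, and it differs from the corresponding item in section 6, although both lists carry the same obligation to stop at once. One of the four items in section 4.7 is affected; the other three agree with section 6. The differences in spasticity and in product scope are secondary.

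The conclusion rests on a literal reading of both lists and on their being current text; nothing marks either as superseded or incomplete. How often swelling would occur cannot be judged from the documents. The consequence is for participant safety and for stopping the device consistently. Sample size, power and error rates are untouched. The remedy is cheap and should be made, but the design does not depend on it.

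**What to change.** The investigator should reconcile sections 4.7 and 6 into a single stop list, state which stimulation arms that list covers (Fesia Grasp, Globus Elite or both), and have both sections refer to it. In doing so, the swelling item and the presence or absence of the spasticity item each need a deliberate decision. Which clinical rule is right is for the investigator to decide, and none is proposed here. The change costs wording only; it alters no assessment, analysis or sample size.
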